#### 9.1.3 Expectedness

The expectedness of an adverse event should be determined based upon existing safety information about the study procedures. Therefore, the following definition will be used:

Confidential Page 31 of 60

- *Unexpected*: An adverse event that is not listed in the safety information available for the study procedure at the specificity or severity that has been observed.
- *Expected*: An adverse event that is listed in the safety information available for the study procedure at the specificity and severity that has been observed.
- *Not Applicable*: Any adverse event that is unrelated to the study procedure.

#### 9.2 Serious Adverse Events

An adverse event is considered serious if, in the view of either the investigator or Sponsor, it results in any of the following outcomes:

- Death;
- A life-threatening adverse event;
  - Note: An adverse event is considered "life-threatening" if, in the view of either the investigator or sponsor, its occurrence places the patient or subject at immediate risk of death. It does not include an adverse event that, had it occurred in a more severe form, might have caused death.
- Inpatient hospitalization or prolongation of existing hospitalization;
  - Note: The term "inpatient hospitalization" refers to any inpatient admission (even if less than 24 hours). For chronic or long-term inpatients, inpatient admission includes transfer within the hospital to an acute/intensive care inpatient unit. Inpatient hospitalization does not include: emergency room visits; outpatient/same-day/ambulatory procedures; observation/short stay units; rehabilitation facilities; hospice facilities; nursing homes; or clinical research/phase 1 units.
  - Note: The term "prolongation of existing hospitalization" refers to any extension of an inpatient hospitalization beyond the stay anticipated or required for the reason for the initial admission as determined by the investigator or treating physician.
- A persistent or significant incapacity or substantial disruption of the ability to conduct normal life functions;
  - Note: A serious adverse event specifically related to visual threat would be interpreted as any potential impairment or damage to the subject's eyes (e.g., hemorrhage, retinal detachment, central corneal ulcer or damage to the optic nerve).

Confidential Page 32 of 60

#### • A congenital anomaly/birth defect.

Important medical events that may not result in death, are life-threatening, or require hospitalization may be considered serious when, based upon appropriate medical judgment, they may jeopardize the patient or subject and may require medical or surgical intervention to prevent one of the outcomes listed in this definition.

# 9.3 Procedures for Reporting Adverse Events

All adverse events and their outcomes must be reported to and the IRB as required by the IRB, federal, state, or local regulations and governing health authorities and recorded on the appropriate source document.

#### 9.3.1 Reporting a Suspected Unexpected Adverse Reaction

All adverse events that are related (definite, probable, possible) and 'unexpected' are to be reported to and the IRB as required by the IRB, federal, state, or local regulations and governing health authorities.

#### 9.3.2 Reporting a Serious Adverse Event

To ensure subject safety, all serious adverse events, regardless of relationship to the investigational product, must be immediately reported. All information relevant to the serious adverse event must be recorded on the appropriate source documents. The investigator is obligated to pursue and obtain information requested by in addition to that information reported on the source document. All subjects experiencing a serious adverse event must be followed up and the outcome reported.

In the event of a serious adverse event, the investigator must notify immediately; obtain and maintain in his/her files all pertinent medical records, information, and medical judgments from colleagues who assisted in the treatment and follow-up of the subject; provide with a complete case history and inform the IRB of the adverse event within their guidelines for reporting serious adverse events.

Contact information for reporting serious adverse events (SAEs):

Confidential Page 33 of 60

# 9.4 Procedures for Unmasking Study Drug

All subjects, investigators, and study personnel involved with the conduct of the study will be masked with regard to treatment assignments. When medically necessary, the investigator may need to determine what treatment arm has been assigned to a subject. When possible (i.e., in non-emergent situations), and/or the study sponsor should be notified, when possible, before unmasking study drug as described in the following paragraph.

If an investigator identifies a medical need for unmasking the treatment assignment of a subject, he/she should contact and/or the medical monitor prior to unmasking the identity of the IP, if possible. Will ask the site to complete and send them the Unmasking Request Form. Will notify Aldeyra and jointly will determine if the unmasking request should be granted. They may consult the medical monitor as needed. The result of the request will be documented on the Unmasking Request Form. If approval is granted to unmask a subject, written permission via the Unmasking Request Form will be provided to the investigator. The investigator will unmask the subject via IWRS. The investigator will complete the Unmasking Memo form and include it in the subject's study file and provide a copy for the Trial Master File (TMF). For each unmasked request, the reason, date, signature, and name of the person who unmasked the subject, must be noted in the subject's study file.

# 9.5 Procedures for Reporting Adverse Events

Adverse events that are ongoing at the end of the study visit will be followed. Phone calls will be placed with any subject who experiences an adverse event until the issue is resolved or the condition is considered ongoing and stable.

#### 10 STATISTICAL HYPOTHESES AND METHODS OF ANALYSES

#### **10.1 Analysis Populations**

[figure not shown]
The following analysis populations will be considered:

- Intent-to-Treat Population The intent-to-treat (ITT) population includes all randomized subjects. Subjects in the ITT population will be analyzed as randomized.
- Per-Protocol Population The per-protocol (PP) population includes subjects in the ITT population who do not have significant protocol deviations and who complete the study. Protocol deviations will be assessed prior to database lock and unmasking. Subjects in the PP population will be analyzed as treated.
- Safety Population The safety population includes all randomized subjects who have received at least one dose of the investigational product. Subjects in the safety population will be analyzed as treated.

Confidential Page 34 of 60

All analyses will be performed for the ITT population and, in addition, on the PP population as sensitivity analyses, as needed. Descriptive statistics of safety data will be calculated for the safety population.

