#### 6 STUDY PARAMETERS

#### 6.1 Primary Endpoint

- Schirmer's Test overall mean change from baseline (CFB) before and after the fourth dose on Day 1
- Schirmer's Test greater than or equal to 10mm responder analysis of change from baseline before and after the fourth dose on Day 1

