#### Visit 2 (Day 1, Baseline and In-Office Dosing)

- Medical/Medication Update
- Adverse Event Query
- Visual Acuity (ETDRS)
- Slit Lamp Biomicroscopy
- Symptom Questionnaires
- Conjunctival Redness Photography
- Inclusion/Exclusion Criteria Review
- Randomization/Enrollment
- Pre-Dose #1 Tear Collection (30 +/- 5 minutes pre-dose)
- In-Office Dose #1
- Post-Dose #1 Tear Collection (started within 10 + 2 minutes of dose) *Wait 3 hours between doses*

Confidential Page 26 of 60

- Pre-Dose #2 Tear Collection (30 +/- 5 minutes pre-dose)
- In-Office Dose # 2
- Post-Dose #2 Tear Collection (started within 10 + 2 minutes of dose) Wait 30 minutes between doses
- In-Office Dose #3
- Conjunctival Redness Photography (10 minutes +/- 2 minutes post-Dose #3)
- Symptom Questionnaires started within 10 minutes + 2 minutes post-

Wait 30 minutes between doses

- Pre-Dose #4 Schirmer's Test (10 +/- 2 minutes pre-dose)
  - Weigh Schirmer's Test strip before and after use
- In-Office Dose #4
- Post-Dose #4 Schirmer's Test (started within 5 +/- 2 minutes of dose)
  - Weigh Schirmer's Test strip before and after use
- Schedule for Visit 3

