# Visit 3 (Day 2, CAE■)

- Medical/Medication Update
- Adverse Event Query
- Urine Pregnancy Test (as needed)
- Visual Acuity (ETDRS)
- Slit Lamp Biomicroscopy
- Conjunctival Redness Photography
- Symptom Questionnaires:

- Pre-Dose #1 Tear Collection (30 +/- 5 minutes pre-dose)
- In-Office Dose #1 within 10 minutes prior to CAE Entry
- CAE Exposure (90 minutes) with:

Confidential Page 27 of 60

- In-Office Dose #2 (45 +/- 2 minutes into CAE exposure, administer by site staff)
- Post-CAE exit Tear Collection (started within 5 + 2 minutes)
- In-Office Dose #3 (started within 2 minutes post-tear collection)
- Symptom Questionnaires started within 10 minutes + 2 minutes post-Dose #3:

- Post-Dose #3 Tear Collection (started within 15 + 2 minutes of dose)
- Slit Lamp Biomicroscopy
- Intraocular Pressure
- Dilated Exam
- Study Exit

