#### **Early Termination/Discontinuation**

If a subject is discontinued from the study prior to Visit 3, then all safety evaluations that are to be performed at Visit 3 should be performed on the day of discontinuation (early termination) or at the discretion of the investigator.

Adverse Events (both elicited and observed) and serious adverse events (SAEs) will be monitored throughout the trial. The investigator will promptly review all adverse events (both elicited and observed) for accuracy and completeness. All adverse events will be documented on the appropriate source document and case report form.

If a female reports a pregnancy or has a positive pregnancy test during the study the investigator will notify immediately. The investigator shall request from the subject and/or the subject's physician copies of all related medical reports during the pregnancy and shall document the outcome of the pregnancy. The investigator will retain these reports together with the subject's source documents and will provide a copy of all documentation to . The pregnant subjects will be discontinued from the trial as per the exclusion criteria.

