# 8.5 Subject Disposition

#### 8.5.1 Completed Subjects

A completed subject is one who has not been discontinued from the study and has completed all applicable assessments.

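### The per-protocol set requires study completion, so subjects whose primary Schirmer's data are already complete on Day 1 can be dropped for later events

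*Combined protocol and SAP*

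**What the plan says.** Section 10.1 (Analysis Populations) limits the PP set to ITT subjects "who do not have significant protocol deviations and who complete the study". It plans all analyses on ITT, which is everyone randomized, and adds PP runs as sensitivity analyses where needed. Deviations are reviewed before lock and unmasking.

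Section 6.1 gives two primary endpoints: "Schirmer's Test overall mean change from baseline (CFB) before and after the fourth dose on Day 1" and "Schirmer's Test greater than or equal to 10mm responder analysis of change from baseline before and after the fourth dose on Day 1". In Section 8.3.1, the last measurement that either one needs is listed under Visit 2: "Post-Dose #4 Schirmer's Test (started within 5 +/- 2 minutes of dose".

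Visit 3, on Day 2, then brings further dosing, the 90-minute CAE, tear collection (for example "Post-CAE exit Tear Collection (started within 5 + 2 minutes"), questionnaires, eye examinations and study exit. The early termination paragraph provides for subjects who leave in between: "If a subject is discontinued from the study prior to Visit 3".

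Section 8.5.1, under Subject Disposition, states: "A completed subject is one who has not been discontinued from the study and has completed all applicable assessments". Section 10.1 does not refer to it.

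**The concern.** A PP analysis of a Day 1 endpoint should show what happens when the comparison is limited to subjects treated and measured as planned up to that endpoint. The completion condition adds a filter that acts after the outcome has been recorded. Whether a subject returns on Day 2 cannot change a Schirmer's reading taken the day before, and it carries no information about whether the four Day 1 doses were given.

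Returning may nevertheless depend on treatment, for example through poor tolerability of the drops. If it does, the filter selects differently in the two arms. A gap between the ITT and PP results could then arise from this rule alone, and a reader could not separate it from the effect of deviations. Reviewing deviations while masked does not prevent this, because completion itself can differ by arm.

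**Working it through.** **Step 1: timing.**

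| Item | When settled | Source |
|---|---|---|
| Both primary endpoints | Day 1, minutes after Dose #4 | Sections 6.1 and 8.3.1 (Visit 2) |
| Study exit | Day 2, after the CAE and eye examinations | Section 8.3.1 (Visit 3) |
| PP membership | Only once the study is completed | Section 10.1 |

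A subject discontinued between the first two rows has complete primary data but fails the third. This holds however completion is defined. If completion is also read through Section 8.5.1, a subject who reaches exit but missed an applicable Day 2 item could fail too.

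**Step 2: is there a figure to reproduce?** No. The readable text gives no dropout rate, standard deviation, effect size or power. Everything below is an illustration on assumed inputs.

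**Step 3: subjects removed.** Let p1 and p0 be the proportions lost after the Day 1 readings on reproxalap and vehicle. Assume p1 = 5-10% and p0 = 2-3%. With n per arm, the number removed is n(p1 + p0). Section 5.1 gives about 350 in total, so n = 175 at 1:1. Section 4 gives about 150 per arm, which implies 300. The two do not agree, so both are shown.

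**Step 4: shift in the PP difference.** Let d be the amount by which excluded subjects differ from retained subjects in the same arm, assumed to be 2-4 mm and equal in both arms. An arm's overall mean is (1 - p) × retained mean + p × excluded mean. Retained and overall means therefore differ by p × d, and the treatment difference shifts by d(p1 - p0).

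| p1, p0 | Removed, n = 175 | Removed, n = 150 | Shift, d = 2 mm | Shift, d = 4 mm |
|---|---|---|---|---|
| 5%, 3% | 14 | 12 | 0.04 mm | 0.08 mm |
| 5%, 2% | 12.25 | 10.5 | 0.06 mm | 0.12 mm |
| 10%, 3% | 22.75 | 19.5 | 0.14 mm | 0.28 mm |
| 10%, 2% | 21 | 18 | 0.16 mm | 0.32 mm |

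That is about 12-23 of 350 subjects (about 11-20 of 300) and a shift of 0.04-0.32 mm. The direction depends on which arm loses more and on whether those lost did better or worse. The shift is zero if nobody is lost, or if losses are equal and d is the same in both arms. For the responder endpoint the formula is the same, with d replaced by the gap in responder proportion.

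**Step 5: size against sampling error.** With no readable SD, express the gap as 0.5-1 SD (assumed). The shift is then 0.5 × 0.02 = 0.01 SD up to 1 × 0.08 = 0.08 SD. The standard error of a difference at 175 per arm is √(2/175) = 0.107 SD, so the shift is about 0.09-0.75 standard errors. The loss of precision is minor: 10% loss in both arms raises the standard error by a factor of 1/√0.90 = 1.054.

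**The case against.** - **No confirmatory result depends on it.** ITT includes every randomized subject, and PP runs are made only where needed. This stands and limits the point to a sensitivity analysis. Nor can PP be called the only check on the primary result: the missing-data and primary-analysis text is largely unreadable, so others may be planned.
- **A reader might infer that PP requires every assessment through Day 2, so that one missed questionnaire excludes a subject.** The documents do not establish this. Section 10.1 asks only for study completion and does not cite Section 8.5.1, which itself speaks of applicable assessments. Reading the two together is reasonable but not certain. A missed questionnaire also has no evident link to Day 1 tear volume, so the 2-4 mm gap should not be assumed for such subjects. The point for subjects who discontinue does not need this reading.
- **The SAP governs.** The Synopsis and Section 10.4.2 say so, and no separate SAP text is readable. A refined PP definition there cannot be ruled out.
- **Every PP set conditions on post-randomization events, including the one proposed here.** True: the change does not restore a randomized comparison. It only removes conditioning on events that cannot bear on the Day 1 endpoints.
- **One set for all endpoints is simpler.** Three of the five endpoints visible in the testing sequence use Day 2 data, so a completer set is understandable. It still fits the two primary endpoints poorly.

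**Conclusion.** The point holds as a minor weakness in a supporting analysis. As written, Section 10.1 drops subjects with complete primary data who discontinue after the Day 1 Schirmer's readings. A missed Day 2 item could have the same effect if completion takes its meaning from Section 8.5.1. A reader might go further and infer that the primary conclusion is at risk. The documents do not support that, because the ITT inference is untouched.

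The likely size is small. The figures above rest wholly on assumed loss rates, an assumed imbalance against reproxalap and an assumed gap in outcome. Only about one day separates the primary outcome from study exit, so actual losses may be lower. The change is worth making because it is cheap and would make any difference between the ITT and PP results easier to interpret.

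**What to change.** In Section 10.1, and in the SAP if it uses the same definition, replace the completion clause with a condition specific to each endpoint:

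- **Day 1 Schirmer's endpoints:** ITT subjects who received the four Day 1 doses, have both Dose #4 Schirmer's readings, and have no significant deviation affecting those readings.
- **Endpoints that use Day 2 data:** additionally require the Day 2 dosing and the assessments that enter that endpoint.

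If the SAP already defines PP in this way, align Section 10.1 with it. Make the change before database lock and unmasking. It affects analysis definitions only, not study conduct. The cost is a few words, one extra population flag, and two PP denominators to label in the tables.

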#### **10.2** Statistical Hypotheses

#### 10.4 Statistical Analysis

#### 10.4.1 General Considerations

Quantitative variables will be summarized descriptively using number of subjects (n), mean, standard deviation, median, minimum, and maximum. Qualitative variables will be summarized using counts and percentages.

All summaries will be presented by treatment group. Summaries will be provided for demographics, baseline medical history, concurrent therapies, and subject disposition.

For the purpose of summarization, medical history, concurrent therapies, and adverse events will be coded to MedDRA and WHODrug dictionaries, as appropriate.

Baseline measures are defined as the last non-missing measure prior to the initiation of randomized study treatment at Day 1. Change from baseline will be calculated as follow-up visit value minus baseline value. Treatment comparisons between active and vehicle calculated as active minus vehicle.

Confidential Page 35 of 60

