#### 4 OVERALL STUDY DESIGN

ADX-102-DED-023 is a Phase 3, multi-center, randomized, double-masked, parallel design, vehicle-controlled trial designed to evaluate the efficacy and safety of 0.25% Reproxalap Ophthalmic Solution compared to vehicle in subjects with dry eye disease. Approximately 350 subjects will be enrolled in the study. Male and female subjects at least 18 years of age with a subject-reported history of dry eye disease in both eyes and meeting all other eligibility criteria will be randomized to receive reproxalap or vehicle in a 1:1 ratio (approximately 150 subjects in each treatment group).

Visit 1 (Day -14 -16/+ 2): Screening	
 
Informed Consent
 
Demographics, Medical/Medication & Ocular History
 
Urine Pregnancy Testing (as needed)
 
Symptom Questionnaires, Ocular Dryness VAS, Visual Acuity
 
Slit Lamp Exam with Conjunctival Redness assessment
 
CAE exposure (90 minutes) with Ocular Dryness VAS, and Conjunctival Redness Assessment
 
Slit Lamp Exam with Conjunctival Redness assessment
 
Schirmer's Test
 
IOP and Dilated Fundoscopy
 

Visit 2 (Day 1): Randomization/Baseline	
 
Medical/Medication Update: AE Query
 
Visual Acuity
 
Slit Lamp Exam
 
Symptom Questionnaires at specified time points
 
Conjunctival Redness at specified time points
 
In-Office Doses (QID)
 
Tear Collection & Schirmer's Test at specified time points
 

Visit 3 (Day 2): CAE	
 
Medical/Medication Update: AE Query
 
Urine Pregnancy Testing (as needed)
 
Visual Acuity, Slit Lamp Exam
 
Symptom Questionnaires
 
Conjunctival Redness at specified time points
 

Confidential Page 18 of 60

CAE exposure (90 minutes) with Ocular Dryness
VAS, and and
Conjunctival Redness Assessments
Tear Collection at specified time points
IOP and Dilated Fundoscopy
Study Exit

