#### 5.4 Exclusion Criteria

#### Each subject may not meet any of the following criteria:

- 1. Clinically significant slit lamp findings at Visit 1 that may include active blepharitis, meibomian gland dysfunction (MGD), lid margin inflammation, or active ocular allergies that require therapeutic treatment, and/or in the opinion of the investigator may interfere with study parameters;
- 2. Diagnosis of an ongoing ocular infection (bacterial, viral, or fungal), or active ocular inflammation at Visit 1;
- 3. Contact lens use within 7 days of Visit 1 or anticipate using contact lenses during the trial;
- 4. Artificial tear eye drop use within 2 hours of Visit 1 or within 24 hours of Visit 2 (drops cannot be used on the day of Visit 2 or Visit 3;
- 5. Previous laser-assisted *in situ* keratomileusis (LASIK) surgery within the last 12 months;
- 6. Cyclosporine 0.05% or 0.09% or lifitegrast 5.0% ophthalmic solution use within 90 days of Visit 1;
- 7. Systemic corticosteroid therapy or other immunomodulator (not including inhaled corticosteroids) within 14 days of Visit 1 or anticipate such therapy throughout the study period;
- 8. Planned ocular and/or lid surgeries over the study period or any ocular surgery within 6 months of Visit 1;
- 9. Temporary punctal plugs during the study that have not been stable within 30 days of Visit 1;
- 10. Use of and unwillingness to discontinue topical ophthalmic prescriptions (including medications for glaucoma) or over-the-counter (OTC) solutions (not including artificial tears), gels or scrubs for the duration of the trial (excluding medications allowed for the conduct of the trial);
- 11. Corrected visual acuity greater than or equal to logarithm of the minimum angle of resolution (logMAR) + 0.7 as assessed by Early Treatment of Diabetic Retinopathy Study (ETDRS) scale in both eyes at Visit 1;
- 12. Pregnancy, nursing, or planned pregnancy during the conduct of the trial;
- 13. Unwillingness to submit a urine pregnancy test at Visit 1 and Visit 3 (or early termination visit) if of childbearing potential. (Nonchildbearing potential is

Confidential Page 20 of 60

- defined as a woman who is permanently sterilized [e.g., has had a hysterectomy or tubal ligation], or is post-menopausal [without menses for 12 consecutive months]);

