#### **8.3** Examination Procedures

# 8.3.1 Procedures to be Performed at the Study Visit with Regard to Study Objective(s)

#### Visit 1 (Day -14 -16/+2, Screening)

- Informed Consent and HIPAA
- Demographics (e.g., gender, date of birth, race, ethnicity)
- Medical/Medication & Ocular History
- Urine Pregnancy Test (as needed)
- Symptom Questionnaires:

Confidential Page 25 of 60

- Ocular Dryness Visual Analog Scale
- Visual Acuity (ETDRS)
- Slit Lamp Biomicroscopy with Conjunctival Redness assessment
- Fluorescein Staining
- Inclusion/Exclusion Criteria Review
- \_\_\_\_
- CAE Exposure (90 minutes, with:
- Slit Lamp Biomicroscopy with Conjunctival Redness assessment
- Schirmer's Test
- Intraocular Pressure
- Dilated Exam
- Schedule for Visit 2

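### Is the baseline for the two Schirmer primary endpoints left undefined?

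*Combined protocol and SAP*

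**What the plan says.** - Section 6.1 gives the first primary endpoint as "Schirmer's Test overall mean change from baseline (CFB) before and after the fourth dose on Day 1". The second applies a 10 mm responder cut-off to the same change. Neither names the visit or time of the baseline reading. They are tests 1 and 2 of the fixed sequence in section 10.4.4.
- Section 10.4.1 sets one rule for all measures: "Baseline measures are defined as the last non-missing measure prior to the initiation of randomized study treatment at Day 1". It then defines change as the later visit's value less that baseline.
- Section 8.3.1 heads the Day 1 visit "Visit 2 (Day 1, Baseline and In-Office Dosing". The Schirmer's Tests visible there are "Pre-Dose #4 Schirmer's Test (10 +/- 2 minutes pre-dose" and "Post-Dose #4 Schirmer's Test (started within 5 +/- 2 minutes of dose". Both come after Doses #1 to #3.
- At Visit 1, sections 4 and 8.3.1 list a Schirmer's Test after the CAE ("CAE exposure (90 minutes) with Ocular Dryness VAS, and Conjunctival Redness Assessment" in section 4, "CAE Exposure (90 minutes, with" in section 8.3.1).
- Exclusion criterion 4 in section 5.4 bars "Artificial tear eye drop use within 2 hours of Visit 1 or within 24 hours of Visit 2".
- The synopsis and section 10.4.2 give the SAP precedence over the protocol's statistical text. The SAP, the primary-analysis and estimand text, and the content of Appendix 1 are blacked out or absent in the public version.

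**The concern.** A reader who starts from section 6.1 meets three pointers that do not obviously agree. The general rule leads back to a screening test taken after an environmental exposure and under a short artificial-tear restriction. The visit label suggests Day 1. The wording about the fourth dose resembles the tear RASP endpoint in section 6.4, which is a change across a dose, so 6.1 might be taken to mean the same.

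The stake would be the quantity estimated by the first two tests, on which all later tests depend. Write a and b for the active-minus-vehicle differences just before and just after Dose #4. A pre-treatment baseline yields their average, (a + b)/2. A change across Dose #4 yields b - a, which is zero if the first three doses had already produced the whole effect (a = b). Separately, a Visit 1 baseline makes each arm's change a move between two sets of test conditions as well as a response to treatment.

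**Working it through.** The plan states no figure to reproduce here, because the sample-size text is blacked out. The check is a trace of the schedule followed by short algebra.

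**Which readings qualify.** Each Schirmer's Test visible in sections 4 and 8.3.1, set against the rule in 10.4.1:

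| Test | Timing | Randomised doses already given | Can be baseline? |
|---|---|---|---|
| Visit 1, listed after the CAE | Day -14 - 16 = Day -30, to Day -14 + 2 = Day -12 | 0 | Yes |
| Visit 2, before Dose #4 | 10 ± 2 min before the dose | 3 | No |
| Visit 2, after Dose #4 | 5 ± 2 min after the dose | 4 | No |

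With no Day 0, the Visit 1 test falls 12 to 30 days before Day 1. One visible reading qualifies, so the rule gives one answer.

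**Could the endpoint be the change across Dose #4?** Four points in the text go against it.

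1. Section 10.4.1 requires a value taken before randomised treatment starts; the pre-Dose #4 reading follows three doses.
2. Section 10.4.1 takes change from baseline to a follow-up visit. The two Dose #4 readings belong to the same visit, 10 + 5 = 15 minutes apart (8 + 3 = 11 to 12 + 7 = 19 with the windows).
3. Section 6.1 asks for an overall mean, as section 6.3 does for measures averaged over time points. A single pre-to-post difference leaves nothing to average.
4. The tear RASP endpoint in section 6.4 describes a change around a dose but does not call it a change from baseline. Section 6.1 does.

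**Does the Visit 2 label conflict with the rule?** No. Redness photography, symptom questionnaires and tear collection are listed at Visit 2 before Dose #1, and for these the rule selects Visit 2. For a measure with no reading before Dose #1 that day, it reaches back to Visit 1.

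**How different are the conditions?** Artificial tears are barred for 2 hours before Visit 1. With the 90-minute CAE in between, and assuming no drops during the visit, the gap at the Schirmer's Test is at least 2 + 1.5 = 3.5 hours, against at least 24 hours for Visit 2.

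**What this does to the mean comparison.** Let B be the Visit 1 reading and Y1, Y2 the readings before and after Dose #4. The change is D = (Y1 + Y2)/2 - B. B precedes randomisation, so its expectation is the same in both arms and

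E(D, active) - E(D, vehicle) = (a + b)/2.

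If the Visit 1 conditions raise or lower B by a common amount s, each arm's mean change moves by -s, and the difference moves by -s - (-s) = 0. Comparing the Day 1 readings without subtracting B also has expectation (a + b)/2, so an extra supportive table would target the same quantity.

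**What this does to the responder comparison.** With no treatment effect, D has the same distribution in both arms whatever the conditions at Visit 1. The chances of reaching 10 mm are then equal and the type I error holds. With an effect, the percentages do depend on s. For illustration only, assume a normal change with SD 8 mm and means of 2 mm (vehicle) and 4 mm (active); the documents give none of these. The responder rate is 1 - Φ((10 - mean + s)/8):

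| s (mm) | Vehicle | Active | Difference |
|---|---|---|---|
| -2 | 1 - Φ(0.75) = 22.7% | 1 - Φ(0.50) = 30.9% | 8.2 points |
| 0 | 1 - Φ(1.00) = 15.9% | 1 - Φ(0.75) = 22.7% | 6.8 points |
| +2 | 1 - Φ(1.25) = 10.6% | 1 - Φ(1.00) = 15.9% | 5.3 points |

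The direction of the comparison is unchanged and its size varies. Naming the reading in section 6.1 would alter none of these values.

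**The case for a change.** The strongest opposing case concerns clarity and precision. An endpoint that controls access to every later test should be readable without inference, and section 6.1 does not refer to 10.4.1. A reading taken weeks earlier under other conditions may also track the Day 1 values less closely than a same-day reading would, which costs precision if the analysis does not adjust for baseline.

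Part of this stands. A sentence in 6.1 naming the reading would be harmless, and the 10 mm cut-off does depend on which reading is subtracted. But a general definition need not be repeated in each endpoint: none of the endpoints listed in sections 6.1, 6.3 and 6.4 names its baseline reading. The precision cost cannot be sized, because the documents give neither the SD nor the correlation and the model text is blacked out. Wording would not reduce that cost. The only step that might is a Schirmer's Test before Dose #1. That would put a further procedure close to the pre-dose tear RASP, redness and dryness readings on Day 1, and dryness over Days 1 and 2 is fifth in the fixed sequence. Leaving it out is a fair trade-off.

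**Conclusion.** The concern does not call for a change. The schedule facts behind it are right, but section 10.4.1 already settles the baseline, and the visible text leaves one qualifying reading, the Visit 1 test. Reading the endpoint as a change across Dose #4 is excluded by the same section.

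The effect on the expected between-arm mean difference is 0 mm, and the type I error is unaffected for both primary endpoints. The residue is descriptive: within-arm mean changes and responder percentages should not be read as treatment response alone. That is the purpose of the vehicle arm, and the hypothesis in section 3 is reproxalap against vehicle.

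This rests on two assumptions: that Visit 1 readings are unaffected by later allocation, as randomisation at Visit 2 ensures, and that the unseen SAP either follows 10.4.1 or names another pre-treatment reading. In either case the mean comparison has the same expectation.
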